5.2 Inclusion criteria for Sarcoidosis

- Adult male or female patients aged 18 years and over
- Women of childbearing age should not be pregnant, planning to get pregnant or breast-feeding.
- Clinical symptoms, CT scan and biopsy diagnosis of sarcoidosis
- Patients with lung parenchymal disease and pulmonary stage II or more
- Recent lung function criteria
 - FVC > 50% predicted
 - DLCO > 40% predicted

5.3 Inclusion criteria for Healthy Volunteers

- Age between 40 to 85 years, age and sex to match the group with IPF
- Healthy subjects without any diseases that may cause inflammation
- Women of childbearing age should not be pregnant, planning to get pregnant or breast-feeding.
- Currently non-smokers: see exclusion criteria

5.4 Exclusion Criteria

5.4.1 Exclusion Criteria for probable IPF and Sarcoidosis Patients

Respiratory Conditions other than IPF or sarcoidosis:

- Confirmed diagnosis of occupational lung disease
- Drug-induced lung disease or hypersensitivity pneumonitis
- Lung and systemic autoimmune disease including connective tissue disease. Patients with an auto-immune profile considered diagnostic for a specific connective tissue disease will be excluded, even in the absence of systemic symptoms. Non-specific rises in auto antibodies e.g. rheumatoid factor; anti-nuclear antibody etc. will not be used to exclude individuals from the study.
- Asbestosis or other asbestos related disease (pleural plaques, mesothelioma, asbestos pleural effusions)
- Granulomatous lung disease.
- Pulmonary artery hypertension (PAH) requiring a specific treatment.
- Predominant chronic obstructive pulmonary disease (COPD) with forced expiratory volume in 1 second /forced vital capacity (FEV1/FVC) < 0.70.
- Patients with active tuberculosis or incompletely treated latent tuberculosis infection
- Lung cancer
- Upper respiratory tract infections in the past 6 weeks.

Systemic Conditions

- History of vasculitis, autoimmune or connective tissue disease
- Known human immunodeficiency virus (HIV) or chronic viral hepatitis
- Clinically significant diseases (other than IPF or sarcoidosis) that may alter respiratory biomarkers: including other respiratory, gastrointestinal, endocrine, haematological, cardiovascular, genitourinary, skin or neurological diseases.
- Recent or ongoing malignant diseases.
- Significant nasal anatomical defects preventing nasal sampling: including hypertrophy of turbinates, major septum deviation, nasal polyposis or recurrent sinusitis and nasal mucosal defects

Bronchoscopy Contraindications

Any contra-indication to bronchoscopy as set out in British Thoracic Society guidelines (34)

Smoking

A detailed smoking history will be taken from all participants: to include total pack years, smoking in the past year, and smoking in the past 2 weeks.

The history will include cigarettes, pipe smoking, cigars, vaping, and shisha.

Any form of smoking is not permitted within 2 weeks of bronchoscopy.

5.4.2 Exclusion Criteria for Healthy Volunteers

- Current inflammatory/ immunological conditions. Any clinically significant diseases that may alter respiratory biomarkers: including respiratory, gastrointestinal, endocrine, haematological, cardiovascular, genitourinary, skin or neurological diseases.
- Recent or ongoing malignant diseases.
- Significant nasal anatomical defects preventing nasal sampling: including hypertrophy of turbinates, major septum deviation, nasal polyposis or recurrent sinusitis and nasal mucosal defects
- Upper respiratory tract infections in the past 6 weeks.
- Cigarette smoking:
 - no cigarettes in the last 2 weeks
 - not more than 10 cigarettes in the past year
 - <10 year lifetime pack history of smoking

5.4.3 Drug Therapy and Concomitant Medication

The following therapy is not allowed for all study population groups:

- Any drugs that may in the opinion of the investigators influence biomarkers of inflammation and fibrosis.
- Pirfenidone, azathioprine, cyclophosphamide, cyclosporine A, oral steroids, Methotrexate, chemotherapy for 3 months
- Treatment with anticoagulant and anti-platelet therapy
- Inhaled steroids for 7 days
- Prescribed anti-inflammatories, salicylates, indomethacin within 7 days

- Over-the-counter (OTC) medications taken within 7 days

5.5 Withdrawal Criteria

Any clinically significant side effects during procedures or withdrawal of consent by the patient /volunteer will necessitate study withdrawal. Patients /Participants will be informed that withdrawal from the study will not affect the care they receive now or in the future and that they are permitted to ask for all previously retained identifiable samples to be destroyed. However, we will inform participants that any samples collected prior to withdrawal will still be used unless they specifically ask for destruction of these samples

All clinical activities will discontinue if there are adverse events related to the sampling procedures performed as part of the study as judged by the, Study Physician and/or the Principal Investigator. In this case participants will be followed up to optimum resolution of the adverse event. If a participant lost capacity to consent during the study, they would be withdrawn from the study. Identifiable data or tissue already collected with consent would be retained and used in the study. No further data or tissue would be collected or any other research procedures carried out on or in relation to the participant.

6 ADVERSE EVENTS

6.1 Definitions

Adverse Event (AE): any untoward medical occurrence in a patient or clinical study subject.

Serious Adverse Event (SAE): any untoward and unexpected medical occurrence or effect that:

- Results in death
- Is life-threatening - *refers to an event in which the subject was at risk of death at the time of the event; it does not refer to an event which hypothetically might have caused death if it were more severe*
- Requires hospitalisation, or prolongation of existing inpatients' hospitalisation
- Results in persistent or significant disability or incapacity
- Is a congenital anomaly or birth defect

Medical judgement should be exercised in deciding whether an AE is serious in all situations. Important AEs that are not immediately life-threatening or do not result in death or hospitalisation but may jeopardise the subject or may require intervention to prevent one of outcomes listed in the definition above, should also be considered serious.

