12 PUBLICATION POLICY27

1 INTRODUCTION

Idiopathic Pulmonary Fibrosis (IPF) is a progressive and incapacitating lung disorder that has a variable clinical course, but is generally fatal within a few years (1, 2). The diagnosis of IPF is based on clinical features, lung function tests showing interstitial disease (decreased transfer of carbon monoxide) and usual interstitial pneumonia (UIP) on high resolution computerised tomography (HRCT) scan of the lung fields (3, 4). As part of their diagnostic work up, most patients with probable IPF require bronchoscopy for taking broncho-alveolar lavage (BAL) samples.

Therapy for IPF is gradually being developed with drugs such as pirfenidone (5) and nintedanib (6) showing modest effects. However, the variable and pleiotropic nature of IPF suggests that combination and personalised therapy will be required (7). In recent years, there have been extensive efforts to measure blood biomarkers in this disease, and a number of blood biomarkers have been described in IPF:

- MMP-7, ICAM-1, VCAM-1, CXCL8/IL-8, S100A12 (8)
- surfactant proteins (SP)-A & D (9, 10)
- periostins (11)
- KL6 (12)
- antibodies to heat shock protein (HSP) 70 (13)
- soluble receptor for advanced glycation end products (sRAGE) (14)
- CCL18 (15), CXCL13 (16)
- collagen biomarkers and protease degradation products (collagen neo-epitopes) (17)
- CA19-9 and CA125

Very recently a 52 gene expression profile in blood has been found to be predictive of outcome in IPF (18).

In IPF there is an urgent need to develop new methods for taking lung samples from a bronchoscope to measure mucosal inflammation. Inflammatory mediators in the mucosal lining fluid (MLF) reflect underlying inflammation, but existing bronchoscopic methods (BAL and biopsy) have significant drawbacks.

Bronchosorption involves passing a special medical sampling device down the operating portal of the bronchoscope. Using bronchosorption to obtain samples and identify molecular signatures of respiratory disease, we hope to achieve new fundamental insights and refine the investigation, diagnosis, stratification and monitoring of IPF. We can discover biomarkers to help assess the effects of existing therapies and identify potential targets for novel treatments.

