6.2.2 Serious AES

An SAE form should be completed and faxed to the Chief Investigator within 24 hours. However, relapse and death due to a pre-existing condition, and hospitalisations for elective treatment of a pre-existing condition do not need reporting as SAEs but should be recorded as AEs.

All SAEs should be reported to the Wales RECs 7 Research Ethics Committee where the Chief Investigator considers the event to be:

- 'related', i.e. resulted from the administration of any of the research procedures; and
- 'unexpected', i.e. an event that is not listed in the protocol as an expected occurrence

Reports of related and unexpected SAEs should be submitted within 15 days of the Chief Investigator becoming aware of the event, using the Report of Serious Adverse Event (non-CTIMP) Form. The Chief Investigator must also notify the Sponsor of all SAEs.

**Contact details for reporting SAEs [contact], attention
Please send SAE forms to: Imperial Clinical Respiratory Research Unit
(ICRRU)
St, Mary's Hospital
[name]
Paddington
London
[name]
[contact] (Mon to Fri 09.00 – 17.00)**

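### Section 6.1 makes unexpectedness part of the SAE definition, and 6.2.2 exempts deaths and relapses from pre-existing disease without first requiring the Chief Investigator to consider relatedness to study sampling

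*Combined protocol and SAP*

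**What the plan says.** Section 6.1 gives two definitions. An adverse event is "any untoward medical occurrence in a patient or clinical study subject". A serious adverse event is "any untoward and unexpected medical occurrence or effect that" meets one of five listed outcomes, death among them. Section 6.1 adds that "Medical judgement should be exercised in deciding whether an AE is serious in all situations", and extends seriousness to other important events.

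Section 6.2 asks for all adverse events to be reported. Section 6.2.1, on non-serious events, asks for these to be recorded regardless of expectedness.

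Section 6.2.2 sets out the SAE route. It begins: "An SAE form should be completed and faxed to the Chief Investigator within 24 hours". It then makes an exception: "relapse and death due to a pre-existing condition, and hospitalisations for elective treatment of a pre-existing condition do not need reporting as SAEs". Exempt events are kept on record as ordinary AEs instead. For ethics committee reporting, the Chief Investigator considers whether an SAE was related to the research procedures and whether it was unexpected, the latter meaning "an event that is not listed in the protocol as an expected occurrence". The Chief Investigator must also tell the sponsor of every SAE.

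Section 5.5 has the Study Physician and/or the Principal Investigator judge whether adverse events are related to the sampling procedures, for the purpose of discontinuing clinical activities. The Introduction says of IPF that it "is generally fatal within a few years".

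**The concern.** Expectedness normally decides who must be told about a serious event, not whether the event is serious. Here it appears in both places. Placed in the definition, it acts before the Chief Investigator has seen anything, and the 24-hour form, the relatedness judgement in 6.2.2 and the sponsor notice all depend on an event first being classed as an SAE.

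The exemption in 6.2.2 acts at the same early point. In this population the main study disease is itself a pre-existing condition and is usually fatal. After bronchoscopic sampling, whether a respiratory death reflects the disease or the procedure is the question on which the Chief Investigator's view is most needed. The text allows it to be settled by someone unnamed before the Chief Investigator is informed.

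What is at stake is timely central oversight of serious harm from the research sampling, and the sponsor's knowledge of it.

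**Working it through.** The section states no figure and the point depends on none, so the check consists of setting the rules side by side and following events through them.

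**Step 1. Compare the two definitions in 6.1.** The AE definition has no expectedness condition. The SAE definition has one. As written, an event can satisfy a seriousness outcome and still not be an SAE because it was expected.

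**Step 2. Ask what unexpected means in 6.1.** There are two readings.
- *The 6.2.2 meaning applies.* An event is then unexpected if it is "an event that is not listed in the protocol as an expected occurrence". The protocol text contains no such list, so every event is unexpected. The condition in 6.1 removes nothing, and the test in 6.2.2 is always met.
- *The ordinary meaning applies.* Section 6.1 gives no definition and no cross-reference, so staff may use their own view of what is expected after bronchoscopy. Some serious events can then fail the definition.

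On the first reading the word is idle. On the second it screens out events. The text does not settle which is intended.

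**Step 3. Follow four kinds of event through sections 6.1 to 6.2.2.**
- *(a) Serious, unexpected, not exempt.* Form to the Chief Investigator within 24 hours, sponsor notified, relatedness and expectedness judged, and an ethics committee report within 15 days if both apply.
- *(b) Serious, regarded by the site as expected (second reading).* Not an SAE under 6.1, so none of the steps in (a) is triggered. Nor does it fit 6.2.1, which covers non-serious events. Only the general rule in 6.2 that all AEs be reported still covers it.
- *(c) Death or relapse attributed to a pre-existing condition.* Exempt under 6.2.2 and recorded as an AE. None of the steps in (a) is triggered, on either reading of unexpected.
- *(d) Elective hospitalisation for a pre-existing condition.* Same route as (c), but it raises little doubt about cause.

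Paths (b) and (c) leave the SAE route before the Chief Investigator's relatedness step.

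**Step 4. Look for a provision that brings (b) and (c) back.**
- The medical-judgement sentence in 6.1 concerns seriousness. It does not address expectedness or relatedness.
- The relatedness judgement in 5.5 belongs to the Study Physician and/or the Principal Investigator and serves to stop study activities. It is not linked to SAE reporting.
- Section 6.2 asks for all AEs to be reported and directs questions to the Chief Investigator, but sets no deadline for an event that is not an SAE.

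None of these sends the event to the Chief Investigator or sponsor as an SAE.

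**Step 5. Who is exposed.** Bronchosorption is planned in the 30 patients with probable IPF and the 15 with sarcoidosis, 30 + 15 = 45 of 60 participants, at Visit 1 only. The healthy volunteers have no bronchoscopy.

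**The case against.** The strongest reply is that the only definition of unexpected in the protocol is the one in 6.2.2, that no expected events are listed, and that the condition in 6.1 therefore excludes nothing. That is a fair reading and may be what the authors meant. It would make the wording redundant and not harmful. But 6.1 does not adopt that definition, and the argument leaves the exemption untouched.

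A second reply is that the exemption already turns on cause: a death caused by sampling is not due to IPF and falls outside it. This is right as far as it goes. Someone must attribute cause to use the exemption. What stands is that the text does not say who, and does not require the Chief Investigator to consider sampling as a cause first.

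Several stronger readings should be resisted.
- A reader might infer that 6.2.2 contradicts 6.1 on death. It does not: it is a general criterion followed by a stated exception.
- A reader might infer that these events receive no relatedness review or vanish from the record. Section 5.5 provides a local judgement, and exempt events are kept as AEs.
- A reader might infer that almost all IPF deaths would bypass SAE reporting. That assumes misattribution, and the documents give no mortality rate from which to count deaths.
- A reader might conclude that a list of expected events should be added. With no list, every SAE judged related goes to the ethics committee. A list would create a filter and reduce that reporting.

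**Conclusion.** The point holds as a gap in the safety-reporting rules. As written, a serious event that the site regards as expected, or a death or relapse attributed to pre-existing disease, can leave the SAE route before the Chief Investigator judges relatedness to study sampling. The first part rests on 6.1 being read without the 6.2.2 definition, which its wording permits but does not compel. The second holds on either reading.

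The size cannot be expressed as a number of events, because the documents give neither a complication rate nor a mortality rate. What is lost is specific: the 24-hour form, the 6.2.2 relatedness judgement, and SAE notice to the sponsor. What remains is the AE record and the local judgement under 5.5. No endpoint or analysis is affected. The change should be made because it improves oversight of serious harm at little cost.

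**What to change.** - In 6.1, delete the words that make unexpectedness part of the SAE definition, so that an SAE is an untoward occurrence meeting a seriousness criterion.
- In 6.2.2, keep expectedness only at the ethics committee step. State there that the protocol lists no expected occurrences; no list needs to be added.
- In 6.2.2, add one sentence: the Chief Investigator documents whether the event was related to the research procedures before a death or relapse is exempted as due to a pre-existing condition.

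This takes a short deletion and two added sentences. Sampling, eligibility and analysis do not change. The downside is a few more SAE forms in a study of 60 participants.

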6.2 Reporting Procedures

All adverse events should be reported. Depending on the nature of the event the reporting procedures below should be followed. Any questions concerning adverse event reporting should be directed to the Chief Investigator in the first instance.

6.2.1 Non Serious AES

All such events, whether expected or not, should be recorded.

6.2.2 Serious AES

An SAE form should be completed and faxed to the Chief Investigator within 24 hours. However, relapse and death due to a pre-existing condition, and hospitalisations for elective treatment of a pre-existing condition do not need reporting as SAEs but should be recorded as AEs.

All SAEs should be reported to the Wales RECs 7 Research Ethics Committee where the Chief Investigator considers the event to be:

- 'related', i.e. resulted from the administration of any of the research procedures; and
- 'unexpected', i.e. an event that is not listed in the protocol as an expected occurrence

Reports of related and unexpected SAEs should be submitted within 15 days of the Chief Investigator becoming aware of the event, using the Report of Serious Adverse Event (non-CTIMP) Form. The Chief Investigator must also notify the Sponsor of all SAEs.

**Contact details for reporting SAEs [contact], attention
Please send SAE forms to: Imperial Clinical Respiratory Research Unit
(ICRRU)
St, Mary's Hospital
[name]
Paddington
London
[name]
[contact] (Mon to Fri 09.00 – 17.00)**

7 ASSESSMENT AND FOLLOW-UP

7.1 Visits and study procedures for probable IPF and Sarcoidosis patients

Visit 1

The first visit will be on the day of the scheduled bronchoscopy and the following procedures will be carried out:

- **Medical history:**
Personal details date of birth, next of kin, and gender, ethnicity and contact details will be collected.
- History relating to general health, allergies and drugs (prescription, over the counter and/or herbal medication/ vitamins) will also be collected
- **Smoking History**
A detailed smoking history will be recorded in terms of pack years, start date, current smoking (past 3 months)

- **Physical and nasal examination:**
The study doctor will perform a general physical examination including examination of heart and lungs. In addition, the physician will check the nose to make sure that nasal structure is normal and nasal passages are not blocked.
- **Vital signs:**
Blood pressure, heart rate, respiratory rate and temperature will be checked
Participant's height and weight will be checked
- **Blood:**
As part of the bronchoscopy patients will have a cannula (small tube) inserted into a vein in the arm to administer medications such as sedatives. When this has been inserted a sample of blood sample (approximately 25 ml) will be withdrawn from the tube.
- **Urine Sample:**
Patients will be asked to provide a sample of urine for safety checks and pregnancy testing in women of child bearing age.
- **Nasosorption or nasal mucosal lining fluid absorption:**
We will use a small strip of absorbent material on a handle to soak up fluid from the inside surface of the nostril (see photograph in Figure 1). This will be placed inside the nostril and left for 60 seconds, keeping light pressure with a finger to absorb fluid before being removed. This technique is very gentle and minimises rubbing and brushing inside the nostril.

[figure not shown]

Figure 1: Nasosorption

- **Lung function test: Spirometry**
This is one of the most common lung function tests. It measures how much air the patient can inhale and exhale. It also measures how fast they can empty the air out of their lungs. Spirometry is used to help diagnose breathing problems such as asthma and chronic obstructive pulmonary disease (COPD). This test will only be performed if the doctor feels that it is required
- **Bronchosorption or bronchial lining fluid absorption:**
As the bronchoscope is passed into the airway, a small strip of absorptive paper is placed on the surface of the airway for up to 1 minute in a similar way to the nasal lining fluid absorption (see photograph in Figure 2). This is a new technique and will be performed by an experienced respiratory physician. The sampling device is a

specially designed medical device that has been produced by an authorised medical device company according to Medical Device Manufacturing Standards.

[figure not shown]

Figure 2: Bronchosorption

- **Bronchoalveolar Lavage (BAL):**

During the clinical bronchoscopy, if the doctor intends to collect a bronchial wash sample (BAL), then a small proportion of this fluid will be collected for the study.

Visits 2 and 3

These are follow-up visits, which will take place 3 and 6 months after the bronchoscopy. Both visits will take place at the Imperial College Respiratory Research Unit at St Mary's Hospital, Paddington, London or in the Out -Patient Clinic. Blood, Urine and nasosorption samples will be collected as per visit 1 schedule.

Please see below a summary of study activities

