After a nasal allergen challenge, we have used the technique of nasosorption to absorb mucosal lining fluid from the nose at frequent intervals. Nasosorption uses a small strip of absorbent material on a handle to soak up fluid from the inside surface of the nostril. Nasosorption is a CE marked device that uses medical grade materials and is produced in a specialised medical device manufacturing company. This is placed inside the nostril and left for 60 seconds, keeping light pressure with a finger to absorb fluid before being removed. This technique is very gentle and minimises rubbing and brushing inside the nostril. The material absorbs the fluid and chemicals produced by the nasal cells that can then be extracted and measured. After nasal allergen challenge (NAC) the eluate from nasosorption contains inflammatory mediators, cytokines and chemokines at high detectable levels, and this has been shown after NAC with grass pollen (21, 22), cat allergen (23) and lipopolysaccharide (24). A recent manuscript has described full gene expression changes after NAC with grass pollen (25) In addition, following experimental human rhinovirus (HRV) challenge in asthma patients, nasosorption and bronchosorption were performed to measure IL-15 (26), IL-25 (27), IL-33 (28) and IL-18 (29). A very complete profile of cytokines and chemokines following HRV challenge in asthma has recently been reported (30) (31), and viral load and cytokines have been measured after RSV bronchiolitis of infancy (32). An extensive validation study has been carried out comparing performance of nasosorption with nasal lavage (33).

Bronchosorption:

The Respiratory Medicine group in Imperial College have developed a bronchosorption device that employs a different proprietary medical grade soft fibrous SAM at the tip. The bronchosorption device is now CE-marked and has been used in over 1500 patients and healthy volunteers. Bronchosorption has the advantage of being less invasive and causing less dilution than a bronchoalveolar lavage (BAL). A straw of SAM or synthetic sponge is attached to a leading plastic wire, and placed down a sheath within the operating portal of a bronchoscope. Under direct bronchoscopic vision the SAM is advanced against the mucosa of a main bronchus or segmental bronchus for up to 30 secs, under direct vision the SAM is then withdrawn up the sheath, and MLF eluted from the detached SAM. The eluted MLF may then be analysed for

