4.3 Sampling

For patients diagnosed with probable IPF and Sarcoidosis, BAL will be collected on the day of their scheduled bronchoscopy. Blood, nasosorption (NS), and bronchosorption (BS) samples will also be collected. Furthermore, on the day of their optional 3 and 6 months follow up visits, we shall collect blood and nasosorption (NS) samples. ***It is important to stress that bronchosorption samples must be taken before BAL or bronchial biopsy samples.*** All patients will have had HRCT of the lung and lung function testing (spirometry and DLco) up to 3 months before bronchoscopy sampling. Healthy volunteers will have a single visit with blood and NS sampling - but no bronchial samples.

With regard to possible coronavirus (COVID-19) infection, this clinical research project will meet Policies and Procedures in conjunction with the NHS, Imperial College London and Public Health England (PHE) guidelines. This will include use of Personal Protective Equipment (PPE) with appropriate clinical facilities and procedures. Appropriate precautions will be taken with sample collection, handling and processing.

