8.3 Statistical Analysis

Data and all appropriate documentation will be stored for up to 10 years after the completion of the study, including the follow-up period.

The major data will be levels of mediators: periostin, surfactant protein (SPD), CCL18 and CXCL13 in blood and bronchial lining fluid.

We shall perform a test of distribution of data (Shapiro-Wilks test) to check normality of data to ensure appropriate statistical tests are applied to the data.

We shall make individual x-y plots for mediators displaying levels for each individual subject within the patient groups (Probable IPF and sarcoidosis) and healthy controls

Summary Statistics

- Normal data with graphs with means and standard error of means (SEM)
- Non-normal data with graphs with medians, quartiles and ranges (box-whisker)

Paired or unpaired t-tests/ANOVA (or equivalent non-parametric tests) will be used to compare mediator levels in blood and airway mucosal lining fluid within groups over time or between different groups at a single time point.

Correlations will be performed to compare mediator levels in blood, and upper and lower airway mucosal lining fluid samples and clinical parameters in patient groups and healthy controls.

Other graphical and analyses methods like heat maps, violin plots, clustering, multivariate analyses and ROC curves will be used as appropriate.

A *P* value of <0.05 is considered significant.

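### Recent infection and smoking are screened at entry but neither checked nor recorded at the optional 3- and 6-month visits, so the exploratory over-time comparisons set a screened baseline against unscreened follow-up.

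*Combined protocol and SAP*

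**What the plan says.** The entry criteria for both patient groups (section 5.4.1) exclude "Upper respiratory tract infections in the past 6 weeks". The same section states: "Any form of smoking is not permitted within 2 weeks of bronchoscopy". It also asks for a smoking history that covers the past year and the past 2 weeks.

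The patient schedule (section 7.1.1) has a single bronchoscopy, at Visit 1. Visits 2 and 3 follow at 12–13 and 24–26 weeks. Section 4.3 calls them optional. Section 7.1 gives their content in one sentence: "Blood, Urine and nasosorption samples will be collected as per visit 1 schedule". The schedule adds lung function where clinically indicated. Medical history, smoking history and nasal examination are described under Visit 1 only.

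Section 8.3 plans paired or unpaired t-tests, ANOVA or non-parametric equivalents to "compare mediator levels in blood and airway mucosal lining fluid within groups over time", or between groups at one time point. It mentions no covariate, exclusion or sensitivity analysis for infection or smoking. Healthy volunteers have one visit (section 4.3).

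**The concern.** By screening for recent infection and recent smoking, the protocol treats both as relevant to what it samples. At baseline each patient has met both conditions. At 3 and 6 months nobody is asked. A patient with a cold that week, or one who stopped smoking for the bronchoscopy and then resumed, is compared with their own cleared baseline.

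This is more than added noise. Infection and smoking can be present at follow-up but are removed at baseline by rule, so any effect they have on a mediator enters the within-patient change in one direction. A paired test would count it as change over time, and a reader would tend to attribute it to disease. Nasosorption is the only airway sample at follow-up, and the nose is where a cold acts most directly. With no repeat healthy-volunteer series, the study has no internal measure of background change.

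**Working it through.** **No plan figure to reproduce.** Section 8.1 declines a sample-size calculation, and the documents give no infection rate, smoking rate, effect size or standard deviation. The core of the check is therefore textual.

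**1. Does either entry condition reach the follow-up visits?**
- Smoking: the rule is tied to bronchoscopy, which happens only at Visit 1. The earliest Visit 2 is at 12 weeks, so a 2-week look-back from it starts at week 12 − 2 = 10 and does not touch the baseline window.
- Infection: the rule is an entry exclusion with no visit named. A 6-week look-back from the earliest Visit 2 starts at week 12 − 6 = 6, again wholly after baseline. Clearance at entry says nothing about that period.
- The reference in section 7.1 to the Visit 1 schedule concerns how samples are collected. Neither condition appears in the Visit 1 procedures or in the schedule table; both sit in section 5. The sentence therefore does not bring them forward.
- The COVID-19 paragraph in section 4.3 covers protective equipment, facilities and sample handling. It does not say when a sample is suitable for comparison.

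**2. How many patients might be affected? (assumed rates)**
Assume r upper respiratory infections per person-year at a constant rate. The chance of at least one in 6 weeks is 1 − exp(−r × 6/52):

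| r per year | Chance | Of 30 IPF | Of 15 sarcoidosis | Of 45 |
|---|---|---|---|---|
| 1 | 0.109 | 3.3 | 1.6 | 4.9 |
| 2 | 0.206 | 6.2 | 3.1 | 9.3 |
| 3 | 0.293 | 8.8 | 4.4 | 13.2 |

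By rule the baseline figure is 0. The counts assume that everyone attends. Because the visits are optional, the percentages apply to attenders and the counts are upper limits for each rate. Resumed smoking would be additional and cannot be estimated from the documents.

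**3. What could that do to a paired test? (illustration only)**
A paired t-test was simulated with 20,000 replicates, a two-sided 0.05 level (section 8.3 gives 0.05 but not the sidedness), no true disease change and a change SD of 1. A fraction p of follow-up samples was shifted upward by d SDs of the change. The spurious mean change is p × d. With p = 0 the rejection rate was about 0.05, as it should be.

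| p | Spurious change at d = 1 | Rejection rate, n = 30 | Rejection rate, n = 15 |
|---|---|---|---|
| 0.1 | 0.1 SD | 0.08 | 0.06 |
| 0.2 | 0.2 SD | 0.17 | 0.10 |
| 0.3 | 0.3 SD | 0.30 | 0.16 |

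Over d = 0.5 to 2 and p = 0.1 to 0.3, the rate runs from about 0.06 to 0.65 for n = 30 and from about 0.05 to 0.34 for n = 15. Both p and d are assumptions. The width of the range shows that the size is not known.

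**The case against.** **Part of the information may already be collected.** Section 6 defines an adverse event broadly and asks that all be recorded, so a cold after enrolment could appear there. The smoking history (sections 5.4.1 and 7.1) identifies recent smokers at baseline, which would allow a stratified look. This stands in part. But adverse-event recording sets no 6-week look-back at the visit, a baseline history cannot confirm that smoking resumed, and section 8.3 uses neither.

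**The affected analysis is minor.** The primary outcome compares bronchial fluid between IPF and sarcoidosis, and that fluid is collected only at Visit 1. No secondary outcome in section 3.3 names change over time; the longitudinal comparison appears only in section 8.3, in a study that calls itself exploratory. This stands in full and limits the weight of the point.

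**Stronger readings that a reader might infer, and that the documents do not support:**
- *That the infection rule expressly lapses after bronchoscopy.* Only the smoking rule is tied to the procedure. The infection exclusion names no visit; what can be said is that nothing carries it forward.
- *That the introduction shows a bias of definite size.* It reports that "A very complete profile of cytokines and chemokines following HRV challenge in asthma has recently been reported", and names IL-15, IL-25, IL-33 and IL-18. That is experimental challenge in asthma. IL-33 is on this study's wider panel, but periostin, SPD, CCL18 and CXCL13 are not among the mediators named. An infection 6 weeks earlier also need not act like a cold on the day, and for blood the documents offer nothing on size. A percentage shift in the focus markers would be conjecture.
- *That only samples meeting the entry conditions should form the main longitudinal analysis.* That would cost samples from groups of 30 and 15 with optional attendance. It is a trade-off, and the documents do not settle it.

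**Conclusion.** The gap is real but confined to the exploratory within-group comparisons of nasal and blood mediators over time. Followed as written, the plan compares a baseline screened for infection and smoking with follow-up samples for which neither is known, and has no repeat control series to show background change. The primary outcome and the named secondary outcomes as assessed at baseline are unaffected.

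The direction of the imbalance between visits follows from the design. Its effect on the results is a risk, not a demonstrated error. The 11% to 29% of attenders with a recent infection rests on an assumed 1 to 3 infections per year, and the false-positive rates rest on assumed shifts. It is worth correcting because it is cheap, and because facts not asked at the visit cannot be reliably reconstructed later.

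**What to change.** 1. At Visits 2 and 3, record upper respiratory infection in the past 6 weeks, any respiratory symptoms that day, and smoking in the past 2 weeks, using the entry definitions and the products already listed in section 5.4.1. Add a row to the schedule in section 7.1.1.
2. Take and keep every sample. No visit is deferred or lost.
3. Add a sentence to section 8.3: the longitudinal comparison of nasal and blood mediators uses all samples, with a pre-specified sensitivity analysis that omits affected samples or adjusts for the recorded infection and smoking status.

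The cost is two short questions per visit, the first in two parts, and one additional analysis. If affected samples are omitted, the infection assumption above would leave about 21 to 27 of 30 IPF patients (30 × 0.707 to 30 × 0.891) and 11 to 13 of 15 sarcoidosis patients (15 × 0.707 to 15 × 0.891) at full attendance, before any loss for smoking. The sensitivity analysis would be less precise. It would also not make follow-up conditions identical to baseline in every respect, since other entry conditions are likewise not restated for these visits.
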